4.2 End of Study Definition

The study will be complete when 56 participants have completed the simulated voiding procedure and 22 participants have completed the rewet testing. This study will be considered complete upon issuance of a Clinical Study Report that has been approved by the Clinical Affairs Director.

5 STUDY POPULATION

5.1 Inclusion Criteria

Individuals must meet the following requirements to be enrolled in the trial:

- Individuals >18 years of age
- Individual can dress and undress self with no assistance
- Individuals can ambulate without assistance
- Individual can sit unsupported in a chair or on bedside with no assistance
- Individual can lay supine and propel self up with no assistance
- Individual can lie left/right lateral and propel self up with no assistance
- Individuals who have hip circumference dimensions between 32" and 70" (81–178 cm)

5.2 Exclusion Criteria

Individuals who meet any of the following criteria will not be allowed to participate in this study:

- Individual is sensitive to the components of the study product(s).
- Individual is considered inappropriate by the Principal Investigator (PI).
- Individual has self-reported pre-existing skin condition, such as open sores, sacral pressure injuries, rash and/or compromise of skin integrity.
- Individuals that cannot complete all phases of the study requirements.
- Individual has self-reported issues around the sacral or perineal areas and/or existing burns or surgical wounds
- Individual requires use of an absorbent undergarment or catheter as the primary incontinence management strategy
- Individuals who are pregnant

5.3 Strategies for Recruitment and Retention

Participants will be recruited from a database in which they have agreed to be contacted for studies or through IRB approved advertising. New participant(s) will be recruited if any participant withdraws from or is unable to complete the study, such that the total number of participants who complete the study are 56.

5.4 Early Withdrawal and Replacement

Each participant will remain on the study until they have completed up to four simulated urinary void cycles in each of the 3 positions: supine, sitting, and laying on either left or right side or they are withdrawn for any reason. Participants that withdraw or are withdrawn early will be replaced. Fifty-six participants are required to successfully complete the testing. Twenty-two of the 56 participants will also perform the retest testing procedure.

6 STUDY PROCEDURES AND ASSESSMENTS

Pre-Visit Activities

6.1. FitRight® Wetness Sensing System Procedure Training

- The staff at the site will receive training by a Medline Industries, LP. Clinical Research Associate (CRA) and/or Clinical Product Specialist on the use of the FitRight® System products prior to the start of use.
- The training logistics will be coordinated between the Medline CRA and/or Clinical Product Specialist with the PI and site staff.
- The Medline CRA and/or Clinical Product Specialist will train a site staff member to be the ongoing trainer of other site staff members as needed.
- The trainer will be a delegated site staff member who will be able to identify staff who were not available at Site Initiation training that will be responsible for performing study activities. Training will be done using Medline provided materials and with any needed support from Medline CRA or Clinical Product Specialist.

6.2. Informed Consent

The study staff will obtain written informed consent from the participant. The written consent must be obtained from all participants and documented on an Informed Consent form (ICF) that has received approval by an IRB/Ethics Committee. The ICF must be written in adherence to GCP and must comply with all elements required by United States (U.S.) Food and Drug Administration (FDA) 21 CFR 50.25 and International Conference on Harmonization (ICH) 4.8, state and local regulations, and additional elements relevant to specific study situations (including a statement that Medline Industries, LP. and relevant authorities have access to participant records). A copy of the signed consent will be given to each participant.

6.3. Verification and Eligibility

Delegated study staff will verify the eligibility of the individual for the study, based on the inclusion and exclusion criteria that will be evaluated in the Participant Screening Form (PSF). Reasons for

participant exclusion will also be documented on the PSF. The participant will receive a unique screening number that will be recorded in the PSF. Demographic information of the participants will also be documented in the PSF.

Successfully enrolled participants will be assigned a unique participant identification number based on the order in which they enroll. Participants will be assigned a randomization sequence for right or left side position according to the Randomization Schedule. The Randomization Schedule, case report forms (CRFs), PSF, and other study-related documents will be provided separately to the study personnel.

6.4. Evaluation of Study Products

Rochester Clinical Research site staff will be responsible for recording participants name and participant identification number so that future identification of study participants can be made if necessary. PI/site staff will be responsible for providing Medline CRA with access to the records for all study participants. Prior to the start of the study, the Medline CRA, and product specialist will assist the study site with initial set-up of the technology/software components required. Refer to FitRight® System IFU.

6.4.1. Application of the FitRight Wetness Sensing System

Participants will be measured for their hip circumference. Participants will be given the brief for their size (available sizes are medium-2XL) that corresponds to the circumference measurement. Study staff will use their discretion to select the applicable size. Study staff will record on the CRF which size was provided to the participant. Following the IFU, participants will be given space to privately apply the FitRight® Brief and tubing. Once the brief is on and tubing is in place, study staff will apply exam gloves and assess the brief for correct application. If the brief or tubing needs to be adjusted, participants will be given more time to privately make adjustments. The tubing should be placed directly in the center of the bottom of the brief at the approximate location of urination.

Once the tubing is in place and the brief is applied correctly, participants will be instructed to sit on the bed in a sitting position. If the tubing moves, participants should again adjust the tubing to the correct position. Study staff will then apply the FitRight® Pod to the brief according to the IFU and make sure that the FitRight® App is indicating the Pod is connected. Once the FitRight® Pod and FitRight® App are properly setup, study staff will connect the tubing in the brief to the tubing connected to the funnel system.

6.4.2 Normal Saline Pours

Once the FitRight® System and tubing is properly setup on the participant, the study staff will pour 90 milliliters (mL) of normal saline (first pour) through the funnel system to enter the brief. Study staff will immediately start a calibrated timer for five minutes once the saline drains from the funnel system. After the five minutes, study staff will document whether the brief did or did not trigger an alert. If the brief triggers an alert, the brief passes and the participant is ready for the next brief. If the brief does not trigger an alert, study staff will pour an additional 150mL normal saline (second pour) through the funnel system and will immediately start a calibrated timer for five minutes once the saline drains from the funnel system.

After the five minutes, study staff will document whether the brief did or did not trigger an alert. If the brief triggers an alert, the brief passes and the participant is ready for the next brief. If the brief does not trigger an alert, study staff will pour an additional 120mL normal saline (third pour) through the filtration system and will immediately start a calibrated timer for five minutes once the saline drains from the funnel system.

After the five minutes, study staff will document whether the brief did or did not trigger an alert. If the brief triggers an alert, the brief passes and the participant is ready for the next brief. If the brief does not trigger an alert, the brief fails, and study staff will pour an additional 120mL normal saline (fourth pour) through the funnel system and will immediately start a calibrated timer for five minutes once the saline drains from the funnel system. After the five minutes, study staff will document whether the brief did or did not trigger an alert. No matter if the brief did or did not trigger an alert, the participant will move onto the next brief. The fourth pour, if required, will help to determine if more volume was needed to trigger the alert or if the system was defective.

Participants will remove the brief and apply a new brief (in their appropriate size) with new tubing as outlined in Section 6.4.1. Participants will be asked to lay in a supine position and study staff will perform the same steps as outlined in Section 6.4.2 above. Once participants and study staff have completed all steps in the supine position, participants will remove the brief and apply another new brief (in their appropriate size) with new tubing as outlined in Section 6.4.1. Study staff will refer to the Randomization Schedule to determine the next position the participant will be in (laying on either the left or right side). Study staff will then perform all of the same steps as outlined in Section 6.4.2.

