After five minutes, staff records whether an alert was triggered. Participant will remove brief ^d		X	
All participants will complete steps above. Only the first 22 participant will go on to complete the following steps.			

Participant applies new brief (study staff checks for correct application) and participant is in sitting position. ^a		X	
Study staff pours 360 mL saline into the brief and starts a timer for ten minutes. ^b		X	
After ten minutes, participant removes brief and gives it to the staff. ^c		X	
Staff weighs out at least 10.0 grams filter paper and records the weight. Staff places the filter paper centered on the wet brief and over the acquisition and dryness layer (ADL) places the calibrated weight on the filter paper and starts a timer for one minute.		X	
After one-minute, calibrated weight and filter paper is removed and the filter paper is weighed, and the weight is recorded.		X	
Study staff will complete steps below for all participants.			
Evaluation for adverse events	X	X	X
Participant dismissal			X
^a Study activity will occur after informed consent has been signed and the participant has met all the inclusion criteria and none of the exclusion criteria.			
^b This pour will only occur if the previous pour(s) did not trigger an alert. If the previous pour did trigger an alert the participant will either move to the application of the next brief or the participant will be dismissed if they are at the end of their participation.			
^c If the Pod alerts prior to the fourth pour, it is considered a pass. If it doesn't alert after five minutes post the third pour, it is a failure. Note: There is no minimum pour volume for the first alert.			
^d Whether there was an alert triggered or not, participant will either move to the application of the next brief or the participant will be dismissed if they are at the end of their participation.			
^e This step is part of the rewet testing. Only the first 22 participants enrolled in the study will perform the rewet testing.			

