2.2 Study Product(s)

The investigational product being evaluated in this study is the FitRight® Connect™ Wetness Sensing System that includes the FitRight® Connect™ Pod, FitRight® Connect™ App, FitRight® Connect™ charger/adapter and FitRight® Connect™ Brief.

2.2.1. Product Overview:

The FitRight® Pod is a wearable sensor that monitors adult briefs for wetness and notifies caregivers when a resident becomes wet. In doing so, the FitRight® System may remove the need for caregivers to unnecessarily check residents while simultaneously ensuring residents are changed promptly as required. The FitRight® Pod is reusable and works by attaching to the outside of the FitRight® Brief. From the outside of the brief, the FitRight® Pod is able to monitor for and characterize moisture on the inside of the brief using a technique called impedance sensing.

The FitRight® Pod then transmits information wirelessly to a Wi-Fi enabled tablet. At a glance, caregivers can view the residents under their care, see who is wet and therefore requires immediate attention, and who is dry and shouldn't be disrupted.

2.2.2 Product Description:

The FitRight® System is used to help monitor and alert caregivers when it is appropriate to change the FitRight® Brief. The FitRight® System is composed of a wetness sensing brief, a pod that connects to Wi-Fi, and software that displays alerts on a display (FitRight® App). The FitRight® Brief is a wetness detection brief that is a non-sterile, disposable, single use device with a reusable wetness alert sensor (FitRight® Pod).

The FitRight® System alerts caregivers when a patient has micturated within the FitRight® Brief. An ink-based sensor is printed on the poly backsheet layer of the FitRight® Brief and when urine contacts the ink for a predetermined amount of time, it sends an alert to the FitRight® Pod that is attached on/secured to the outside of the FitRight® Brief. The FitRight® Pod translates that alert (via Wi-Fi) to the software application using a cloud-based server that is loaded on to a display device chosen by the user.

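### Each pour adds saline and at least five minutes together, and no alert time is planned for collection, so results by fluid amount and the fourth pour cannot separate a need for more saline from a slow response

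*Combined protocol and SAP*

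**What the plan says.** Section 2.2.2 explains how the sensor works: "when urine contacts the ink for a predetermined amount of time, it sends an alert to the FitRight® Pod". The length of that contact time is not given anywhere.

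Section 6.4.2 (likewise 1.2 and 4.1) sets a fixed ladder for each brief. It starts when "the study staff will pour 90 milliliters (mL) of normal saline (first pour) through the funnel system to enter the brief". Staff then wait five minutes on a timer started once the funnel has drained. "After the five minutes, study staff will document whether the brief did or did not trigger an alert". The next pour is given only if there was no alert: "If the brief does not trigger an alert, study staff will pour an additional 150mL normal saline (second pour) through the funnel system". A third pour of 120 mL follows on the same terms. If there is still no alert, "the brief fails, and study staff will pour an additional 120mL normal saline (fourth pour) through the funnel system". The purpose given for that last step is: "The fourth pour, if required, will help to determine if more volume was needed to trigger the alert or if the system was defective". Section 4.1 says the same, with the brief rather than the system as the possibly defective part.

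The by-volume reading is part of the plan. Section 8.5.1 codes pass or fail for each fluid step and position, 8.5.3 stratifies the pass and fail percentages by volume, 8.6 puts volume in the primary analysis, and 8.9.1 stratifies reliability by fluid amount and adds a chi-square of fluid amount against test status. The analysis data in 8.3 and 8.6 contain volume, position, alert status and covariates. They do not contain the time of the alert.

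**The concern.** If the alert depends on how long fluid has been in contact with the ink, elapsed time is a cause of the outcome in its own right. The ladder never varies volume without varying time. No brief with a Pod is held at one volume for longer than one waiting period, and none starts at a larger volume. The single 360 mL pour in the rewet test (6.4.3) is done without the Pod, so it cannot help.

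An alert after the second, third or fourth pour may therefore be a late response to saline already in the brief, yet it is booked against the larger volume. Two parts of the plan are at stake. The first is any statement about how the alert rate changes with fluid amount. The second is the reading of a fourth-pour alert, for which the plan allows only two explanations (a volume need or a defect) when a slow but working sensor is a third. Time to alert also bears on the rationale in 2.1, which rests on shortening the time a resident spends in a wet brief.

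**Working it through.** **Inputs.** Pour volumes of 90, 150, 120 and 120 mL, and a five-minute wait after each, from 6.4.2. Contact time: stated to exist in 2.2.2, length not given. I write D for the delay, in minutes from the end of the first drain, until a brief alerts when 90 mL alone is enough (contact time plus wicking to the ink). D is an assumption and is shown as a range.

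**Step 1: reproduce the plan's range.** 90 + 150 + 120 = 360 mL, which matches the upper limit of the stated pass range in 1.1 and 4.1. The fourth pour gives 360 + 120 = 480 mL.

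**Step 2: line up volume and time.** Minimum elapsed time at reading k is 5 × k minutes.

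| Reading | Cumulative volume (mL) | Minimum elapsed time (min) | Scored |
|---|---|---|---|
| 1 | 90 | 5 | pass if alert |
| 2 | 90 + 150 = 240 | 10 | pass if alert |
| 3 | 240 + 120 = 360 | 15 | pass if alert, otherwise fail |
| 4 | 360 + 120 = 480 | 20 | already failed |

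Each volume occurs at one time step only. Across the four readings the Spearman correlation is 1.00 and the Pearson correlation 0.998. Drain times come on top, so the true times are somewhat longer and are not planned to be recorded.

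**Step 3: two opposite sensors, one record.** Sensor V responds only to volume, with thresholds of 60, 200, 300 or 420 mL. Sensor T is wet enough at 90 mL and responds only to time, with delays of 3, 8, 13 or 18 minutes. Reading each against the table, both give first alerts at pours 1, 2, 3 and 4 respectively. The planned data are identical, so no analysis of them can tell V from T. This does not depend on sample size, significance level or the assumed pass rate.

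**Step 4: size, over a range of D.** Take a brief for which 90 mL is enough, ignoring drain time.

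| D (min) | Recorded as | Booked volume minus 90 mL |
|---|---|---|
| up to 5 | alert at 90 mL | 0 |
| over 5 to 10 | alert at 240 mL | 150 |
| over 10 to 15 | alert at 360 mL | 270 |
| over 15 to 20 | fail, then alert at 480 mL | 390 |
| over about 20 | fail, no alert at the fourth pour, read as a defect | not applicable |

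Drain time moves the later boundaries slightly upward, so the cut-offs are approximate.

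**The case against.** The strongest reply is that the main result does not need this separation. Section 8.1 is built on the proportion of successful alerts, and 8.9 makes the percentages passed and failed the key quantity. That result holds whether volume or time set off the alert. Sections 1.2 and 4.1 also say that no minimum volume is required. All of this stands: a reader might infer that the overall pass rate is invalid, and the documents do not support that.

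The fourth pour is described as a help, not a definitive test, and it comes after the brief has failed, so no pass can be gained from it. That is fair. It still offers two explanations where there are three.

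The effect may be small. Nothing in the documents suggests a delay of more than five minutes in a wetted sensor. Equally, nothing rules it out, and the planned data could not show it.

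The CRFs are supplied separately (6.3) and alerts pass through an App and a server (2.2.2), so alert times may exist somewhere. What can be said is only that no section plans to record or use them. Nor do the documents show that drain time differs between positions.

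A reader might also infer from footnote c in 1.2, which ties a pass to the fourth pour and a failure to the third five-minute reading, that an alert arriving between the two is both a pass and a failure. Section 4.1 settles this: a pass needs the alert both inside one of the first three five-minute windows and ahead of the fourth pour.

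**Conclusion.** The point holds as a limit on interpretation and a cheap improvement to the design. The overall result can be reported as an alert within 360 mL and about 15 minutes. The results and chi-square by fluid amount (8.5.1, 8.5.3, 8.9.1) cannot be read as a volume effect alone, and a fourth-pour alert cannot separate a volume need from a slow response.

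That volume and time cannot be separated follows from the procedure itself. Its practical size does not, because it rests on the unstated contact time plus wicking. It is small if that total is well under five minutes. If it is longer, and 90 mL would have been enough, the booked volume is too high by 150 to 390 mL, or the brief is taken as defective.

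**What to change.** 1. In 4.1 and 6.4.2, have staff note the reading on the timer already running when the alert appears (or that it came before the timer started), and the start and end of each drain. Report time to alert alongside volume.
2. In 8.5 and 8.9.1, describe by-pour results as by cumulative volume and elapsed time. This costs nothing and can be done even if enrolment has finished.
3. For a brief already scored as failed after the third pour, wait a further five minutes with no saline and record alert yes or no before the fourth pour. An alert in this hold shows a delayed response without added volume. No alert makes a later fourth-pour alert better evidence of a volume effect, but not conclusive, because that pour still adds 120 mL and five minutes together.
4. Optionally, align the wording of footnote c in 1.2 with the cut-off in 4.1.

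These steps do not fully separate volume from time at the first three pours. That would need some briefs held longer at a fixed volume, or started at a larger volume with the Pod attached. Item 2 covers what remains.

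Cost: a few CRF fields, plus five minutes per failing brief. With 56 × 3 = 168 briefs and the roughly 90% success assumed in 8.1, applied per brief, that is 168 × 0.10 = 16.8, about 17 briefs. At the other rates entered there, 95% and 85%, it is 168 × 0.05 = 8.4 and 168 × 0.15 = 25.2.

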6.4.3 Rewet Procedures

Twenty-two participants enrolled in the study will perform the rewet testing procedures. Participants will apply the sized FitRight® Brief and tubing as outlined in Section 6.4.1 above and study staff will confirm correct application. The FitRight® Pod will not be applied to the brief for this testing. Study staff will pour 360 mL normal saline through the funnel system to enter the brief. Study staff will immediately start a calibrated timer for ten minutes once the saline drains from the funnel system. After the ten minutes, participants will remove the brief and give the brief to the study staff. Study staff will weigh out at least 10.0g filter paper (and as close to 10.0g as possible) and record the weight (in grams). Study staff will apply the filter paper centered on the wet brief and over the ADL layer, apply a calibrated weight to the top of the filter paper, and immediately start a calibrated timer for one minute. After the one minute, the study staff will remove the calibrated weight and filter paper and weigh the wetted filter paper and record the weight in grams to the first decimal point (ie: tenth of a gram). If leakage or fluid related issues are noted, they will be recorded on the CRF. The re-wet test will be considered an invalid test (test failure) if leakage is noted. Additional participants will be tested until 22 valid re-wet tests are completed.

